### 10.1 General Considerations

All statistical tests will be two-sided and statistical significance will be assessed with respect to a nominal p-value  $<0.05$ . Prior to the data base lock, a separate statistical analysis plan (SAP) will be finalized. Any deviations from the planned analyses will be documented and justified in the final clinical/statistical study report. The SAP will detail all planned analyses and will serve as a statistical programming requirements document.

### 10.2 Determination of Sample Size

The objective of the pilot study is to evaluate the safety and feasibility of autologous Adipose-Derived Regenerative Cells (ADRCs) for the treatment of thermal wounds. The sample size of up to 15 subjects (each subject contributing up to 3 wounds to the dataset) is not powered to test specific hypotheses. The sample size is proposed to provide preliminary safety and feasibility data in order to design a larger study with sufficient power to test a hypothesis regarding benefits of ADRCs.

### 10.3 Data Analyses

Safety and efficacy endpoints will be summarized by treatment group using descriptive statistics (n, mean, SD, median, minimum and maximum), for quantitative variables and frequencies and percentages for categorical variables.

For quantitative efficacy variables, the change from baseline to each post-baseline time point will be analyzed using Student's t-test. For each endpoint, the treatment groups will be compared using two-sided tests at the alpha=0.05 level of significance.

The final dataset includes grafts with different mesh size (for example; 2:1 and 3:1). While the study is not powered for analysis of efficacy, data analysis for comparison between subjects receiving usual care and those receiving usual care plus ADRCs with respect to exploratory endpoints associated with healing (e.g.: percent epithelialization, pigmentation, hardness, Vancouver Scar Scale) will be stratified by mesh size (for example: 2:1, 3:1, 4:1, and all grouped).

Subjects randomized to the ADRC-treatment arm who undergo liposuction but who are not treated with ADRCs because the ADRCs do not meet release criteria may be followed up for the full duration of the study. Such subjects will be (a) included in the full data analysis for feasibility, (b) analyzed separately for safety, (c) analyzed in the ITT group for efficacy, and (d) excluded from the PTE group for efficacy.

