Exploratory Endpoints	
 
Transepithelial water loss at weeks 2, 3 and 4 to be performed at 2 different sites within the wound (central and peripheral)
 
Wound pain VAS (visual analogue scale) at time of first dressing change and day 10 and weeks 2, 3 and 4
 
Pruritis VAS at weeks 3, 4, 8, 12, 26 and 52
 
Patient and Observer Scar Assessment Scale (v2.0) at weeks 3, 4, 8, 12, 26 and 52
 
Skin elasticity measurement at weeks 12, 26 and 52
 
Vancouver Scar Scale at weeks 12, 26 and 52
 
Skin pigmentation and hardness at weeks 12, 26 and 52
 
ADRC cell population subtypes (FACS)
 
Biomarkers related to burn injury (such as C-reactive protein (CRP), IL-6, IL8, IL1<math>\beta</math>, interleukin-1 receptor antagonist (IL-1ra); neutrophil gelatinase-associated lipocalin (NGAL); Tumor Necrosis Factor-<math>\alpha</math> (TNF<math>\alpha</math>), and tumor necrosis factor receptor 1a (TNFR-1a)) and related to scarring (such as amino-terminal propeptide of type III procollagen, (PIIINP), TIMP1, MMP2, MMP9 and VEGF-A) will be collected at baseline (prior to treatment), days 6, and 10 and weeks 2, 3, 4, 8, and 12 post ADRC administration. Serum sample will be collected from 4 to 5 ml of whole blood that is centrifuged, separated into 500-<math>\mu</math>L aliquots, and stored at -80°C at the clinical site serum bank or central lab until use.
 
Serum biomarkers will be measured using commercial Enzyme-Linked ImmunoSorbent Assay (ELISA).
 

Statistics	
The intent-to-treat (ITT) population will include all randomized subjects. Randomization will occur on the STSG procedure day prior to liposuction. The per-treatment-evaluable (PTE) population will include all enrolled subjects who have day 6 follow-up information available.
 
The groups compared will be the subjects receiving ADRCs and STSG and the usual care controlled subjects (both grouped and stratified by mesh size). Analysis will be performed by a one way ANOVA.

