##### ***4.6.2 Key Secondary Endpoints***

- Percent epithelialization of the graft at time of first dressing change and day 10 (only if wound dressing change planned) and weeks 2, 3 and 4
- Percent take of the graft at time of first dressing change and day 10 (only if wound dressing change planned) and weeks 2, 3 and 4

Digital photography will be performed at surgery and at each follow-up visit for blinded independent review.

Graft take will be assessed as the area over which vascularization is evident and sufficient anchorage to the underlying tissue exists to support epidermal growth. Take will be expressed as a percentage of the area originally covered by the graft. Percent take should be estimated separately for each graft-treated site.

Both of the above endpoints will be evaluated by (a) visual inspection by the treating surgeon, and (b) standardized digital photography and scoring centrally by a blinded trained assessor.

- Percent of group with complete wound closure at each assessment through to 12 weeks

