#### 4.6.3 *Exploratory Endpoints*

- Transepithelial water loss at weeks 2, 3 and 4
- Wound pain VAS at time of first dressing change and day 10 and weeks 2, 3 and 4
- Pruritis VAS at weeks 3, 4, 8, 12, 26 and 52
- Patient and Observer Scar Assessment Scale (v2.0) weeks 3, 4, 8, 12, 26 and 52
- Skin elasticity (Delfin Elastimeter) measurement at 12, 26 and 52 weeks
- Vancouver Scar Scale at 12, 26 and 52 weeks
- Skin pigmentation (Delfin SkinColorCatch) measurement at weeks 12, 26, and 52
- Skin hardness (Delfin Skin Fibrometer measurement) at weeks 12, 26, and 52
- Biomarkers related to burn injury (such as C-reactive protein (CRP), IL-6, IL8, IL1 $\beta$ , interleukin-1 receptor antagonist (IL-1ra); neutrophil gelatinase-associated lipocalin (NGAL); Tumor Necrosis Factor- $\alpha$  (TNF $\alpha$ ), and tumor necrosis factor receptor 1a (TNFR-1a)) and related to scarring (such as amino-terminal propeptide of type III procollagen, (PIIINP), TIMP1, MMP2, MMP9 and VEGF-A) will be collected at baseline (prior to treatment), days 6, and 10 and weeks 2, 3, 4, 8 and 12 post ADRC administration. Serum sample will be collected from 4 to 5 ml of whole blood that is centrifuged, separated into 500- $\mu$ L aliquots, and stored at -80°C at the clinical site serum bank or central lab until use.
- Serum biomarkers will be measured using commercial Enzyme-Linked ImmunoSorbent Assay (ELISA).

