### 8.3 Burn Evaluations

The physical characteristics of the selected burn areas and the graft (up to 3 per subject) as well as the subjective evaluation of symptoms will be evaluated using several assessment tools. The assessment tools are listed below and detailed information and instructions provided in the *Study Reference Manual*. Planned study days are listed below but an acceptable range of days (±) is in the schedule of events.

- Percent epithelialization at early dressing changes (estimated time of first dressing change and day 10 after graft application and at weeks 2, 3 and 4 (by surgeon evaluation and blinded independent review of standardized photographs)
- Percent take of the graft at early dressing changes (estimated time of first dressing change and day 10 after graft application (if wound dressing must be changed) and at weeks 2, 3 and 4
- Occurrence of complete wound healing at each assessment weeks 4 to 12
- Transepithelial water loss at weeks 2, 3 and 4
- Wound pain VAS at time of first dressing change and day 10 and weeks 2, 3 and 4
- Pruritis VAS at 3, 4, 8, 12, 26 and 52 weeks
- Patient and Observer Scar Assessment Scale (POSAS) at 3, 4, 8, 12, 26 and 52 weeks
- Vancouver Scar Scale at 12, 26, and 52 weeks
- Skin elasticity measurement at 12, 26 and 52 weeks (Delfin SkinElastimeter)
- Skin pigmentation (Delfin SkinColorCatch) measurement at weeks 12, 26, and 52
- Skin hardness (Delfin SkinFibrometer) measurement at weeks 12, 26, and 52

- Percent of wounds with complete wound closure at weeks 2, 4, 8 and 12
- Digital photography of treated wounds on day 1 and each follow up visit
- Biomarkers related to burn injury will be assessed from 4-5mL blood (serum) samples drawn at baseline (prior to treatment), time of first dressing change and day 10 and weeks 2, 3, 4, 8 and 12 post-ADRC administration.

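### The change-from-baseline t-test fixed in section 10.3 cannot be run for eight exploratory measures, which are first taken after treatment

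*Protocol*

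**What the plan says.** Section 10.3 sets one inferential analysis for continuous efficacy outcomes: "For quantitative efficacy variables, the change from baseline to each post-baseline time point will be analyzed using" Student's t-test. The next sentence adds: "For each endpoint, the treatment groups will be compared using two-sided tests at the alpha=0.05 level of significance". A later paragraph of the same section plans an arm comparison, stratified by mesh size, for healing measures and gives as examples "percent epithelialization, pigmentation, hardness, Vancouver Scar Scale". The exploratory measures are therefore within the section's scope. The Statistics row of the Protocol Summary says "Analysis will be performed by a one way ANOVA" and does not name the quantity analysed.

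The timing of the measures is set in sections 4.6.3, 8.3 and 8.8 to 8.10 and in Appendix A. Examples are "Wound pain VAS at time of first dressing change and day 10 and weeks 2, 3 and 4", "Transepithelial water loss at weeks 2, 3 and 4" and "Vancouver Scar Scale at 12, 26 and 52 weeks". Neither the screening list (8.6.1) nor the Day 1 list (8.7) includes any of these. The biomarkers do have a screening sample, and section 4.6.3 and the Appendix A footnote both use baseline for them in the sense of before treatment.

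**The concern.** A change score needs a starting value. If the protocol names change from baseline as the tested quantity and schedules no pre-treatment measurement, the test as written has no data to work on. The SAP can choose a different quantity, but it cannot create measurements that were never taken, and section 10.6 rules out imputation.

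The main risk in leaving the text alone is that a programmer following section 10.3 takes the first available value as baseline. For all eight measures that value comes after treatment. An effect already present at that visit would be subtracted from every later comparison. This matters here because section 6.6 postulates an action that begins early in the injury process.

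**Working it through.** The protocol gives no numerical result to reproduce on this point. The check sets the stated test against the schedule.

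**Step 1. First assessment and number of visits (Appendix A, agreeing with 4.6.3 and 8.8 to 8.10).**

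| Measure | First taken | Pre-treatment value | Scheduled visits |
|---|---|---|---|
| Wound pain VAS | First dressing change | None | 5 (including conditional Day 10) |
| Transepithelial water loss | Week 2 | None | 3 |
| Pruritus VAS | Week 3 | None | 6 |
| POSAS (counted once) | Week 3 | None | 6 |
| Vancouver Scar Scale | Week 12 | None | 3 |
| Skin elasticity | Week 12 | None | 3 |
| Skin pigmentation | Week 12 | None | 3 |
| Skin hardness | Week 12 | None | 3 |
| Serum biomarkers | Screening | Yes | 7 after treatment |

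**Step 2. Comparisons affected.** 5 + 3 + 6 + 6 + 3 + 3 + 3 + 3 = 32, or 32 − 1 = 31 if Day 10 is not held. The four measures that start at week 12 account for 4 × 3 = 12 of these. These are schedule cells, not a count of all tests: water loss is taken at two sites in the wound, POSAS has patient and observer parts, and analyses run by mesh size and in two populations.

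**Step 3. Can the stated quantity be formed?** Write Y(t) for the value at visit t and Y(0) for the pre-treatment value. The tested quantity is D(t) = Y(t) − Y(0). For the eight measures Y(0) is not collected, so D(t) does not exist at any visit. This holds whether the t-test is read as paired within an arm or as two-sample between arms, since both start from D(t).

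**Step 4. What a substitute baseline would do.** Let d(t) be the true difference between arms at visit t, and let visit 1 be the first post-treatment visit. Using Y(1) as baseline, the arms would be compared on Y(t) − Y(1), whose expected difference is d(t) − d(1). The comparison at visit 1 disappears (0 by construction), leaving 32 − 8 = 24 cells. In each of those, any effect present at visit 1 is removed. For the week 12 measures only change after week 12 would be tested.

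**Step 5. The two quantitative key secondary endpoints.** Percent epithelialization and percent take also have no scheduled Day 1 score (5 + 5 = 10 further cells). They are weaker cases. Section 4.6.2 states "Digital photography will be performed at surgery and at each follow-up visit for blinded independent review", section 8.7.2 requires photographs shortly after grafting, and section 10.3.2 already expresses take relative to the grafted area. The observed percentage is the natural quantity for both.

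**Step 6. Measures named in section 10.3 itself.** Of the four given as examples there, none has a scheduled pre-treatment score, and three (pigmentation, hardness, Vancouver Scar Scale) begin at week 12.

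**The case against.** The strongest reply is that only one sentence of section 10.3 mentions change. The sentence after it, the mesh-size paragraph and the Statistics row all describe comparisons between arms without tying them to a baseline. A sensible reader would use change where a baseline exists and observed values elsewhere, and section 10.1 leaves the detail of every analysis to the SAP. Scar scales plainly have no pre-graft value, so a misleading analysis is unlikely, and the measures are exploratory in a study that section 10.2 says is not powered.

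Part of this stands. The other statements do permit a between-arm comparison of observed values, and the low stakes are real. But none of them names a quantity. The only one named is change from baseline, and it is applied to quantitative efficacy variables without qualification. This is a stated analysis that the schedule makes impossible, which is different from detail left to the SAP. Section 10.1 also requires departures from the planned analyses to be documented and justified, so a SAP that does the sensible thing would be departing from the sentence as written.

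The t-test and the one-way ANOVA are not themselves in conflict for a plain two-arm comparison, where the ANOVA F statistic is the square of the pooled two-sample t. What both places lack is a quantity that can be computed for these measures.

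**Conclusion.** The concern holds. As written, the test in section 10.3 cannot be carried out for eight exploratory measures, covering up to 32 scheduled measure-by-visit comparisons (31 without Day 10), 12 of them from measures that begin at week 12. Percent epithelialization and graft take share the gap in a weaker form. No share of all planned tests is given, because the biomarker panel (8 burn-related plus 5 scarring-related = 13 analytes) is listed only as examples.

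The count assumes that POSAS is one measure and that baseline means before treatment, as the protocol uses the word for the biomarkers. The consequence is modest: the primary endpoints and the descriptive summaries by arm do not depend on this sentence. It should still be corrected, because section 10.3.2 counts these p-values towards the evidence on effectiveness and section 10.2 says the pilot is meant to inform a larger study.

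**What to change.** Revise section 10.3 as follows:

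- For wound pain VAS, transepithelial water loss, pruritus VAS, POSAS, Vancouver Scar Scale, elasticity, pigmentation and hardness, compare observed values between arms at each scheduled visit. Do the same for percent epithelialization and graft take.
- Restrict change from baseline to the serum biomarkers, with the screening sample as baseline.
- State that no post-treatment visit serves as baseline for the between-arm test. Descriptive change during follow-up, such as week 12 to week 52, can still be reported.
- Name the same analysed quantity in the Statistics row of the Protocol Summary.

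The cost is wording in two places. No new assessments or visits are needed.

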## 4.3 Sample Size

Up to a total of 15 subjects will be enrolled. Each patient may contribute up to three qualified wound

areas for the analysis. If more than one wound is identified, each must be noncontiguous with the other(s). Therefore, between 15 and 45 wounds will be evaluated. Wound areas that have been treated with a biologic dressing such as Alloderm® or Integra® are not qualified for analysis. However, a wound area that receives excision and grafting as described in this protocol without the application of a biologic dressing may be qualified even if other wound areas in the subject are not qualified because they have been treated with a biologic dressing.

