## 5.2 Randomization and Subject Identification

Randomization to ADRC and usual care will occur within 2 hours prior to the scheduled surgery for STSG.

Randomization will be done via an interactive web response system (IWRS). Subjects will be randomized in a 2:1 ratio to receive intravenous delivery of either Celution® System processed ADRCs with usual care or to usual care alone.

A total of up to 15 subjects will be enrolled. Each patient will contribute up to three qualified wound areas for the analysis. If more than one wound is identified, each must be noncontiguous with the other(s). Therefore, between 15 and 45 wounds will be evaluated.

The 1st 5 subjects enrolled in active treatment will be observed for adverse events over a 7 day period. If no SAEs occur during that period, for that individual subject, the next subject enrolled in active treatment may be entered with the same 7 day observation period. The safety results of the first 5 subjects will be reviewed by the DMC and their evaluation will be used in conjunction with the clinical data collected to date, and if appropriate, to potentially remove the staggering approach to the study. Enrollment after the first 5 subjects enrolled in active treatment may continue only after the DMC has completed its safety review and recommends continuation.

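### The protocol fixes an unadjusted change-from-baseline t-test, which in practice falls on the serum biomarkers; a baseline-adjusted log-scale analysis would usually be more efficient, by an amount the documents do not determine

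*Protocol*

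**What the plan says.** Section 10.3 of the protocol fixes the outcome form and the test: for quantitative efficacy variables, "the change from baseline to each post-baseline time point will be analyzed using" Student's t-test. It adds that "the treatment groups will be compared using two-sided tests at the alpha=0.05 level of significance". The Statistics row of the Protocol Summary names a one-way ANOVA instead. With two groups that is the same test as the two-sample t-test, and it too has no baseline covariate. No transformation is mentioned anywhere.

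Section 4.6.3 lists 13 serum biomarkers, eight related to burn injury and five to scarring. They "will be collected at baseline (prior to treatment), days 6, and 10 and weeks 2, 3, 4, 8 and 12 post ADRC administration", which is one pre-treatment and seven post-treatment draws.

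On size, section 4.3 says "Up to a total of 15 subjects will be enrolled" and section 5.2 sets 2:1 allocation, so a full trial has 10 ADRC and 5 usual-care subjects. Section 10.2 says the sample size "is not powered to test specific hypotheses".

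**The concern.** Section 10.3 does not name the outcomes that its change-from-baseline rule covers. Appendix A settles this in practice. Percent epithelialization, graft take, water loss, wound pain, pruritus, POSAS, Vancouver Scar Scale, elasticity, pigmentation and hardness are all first measured after the procedure. Only the biomarkers have a value from before treatment, so among these outcomes the rule can act only on them.

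A change score subtracts the whole baseline value however weakly baseline predicts follow-up, so it adds noise when the correlation is low and carries chance baseline imbalance into the result. With about five controls, both matter. If concentrations are right-skewed and analysed untransformed, one or two extreme subjects can also dominate a difference in means.

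Two uses of the results are at stake. Section 6.6 puts modulation of inflammation first among the proposed mechanisms, and the serum markers are the listed in-patient measure of it. Section 10.2 says the trial exists to help design a larger study, so an imprecise biomarker contrast is a weaker planning input than the same samples could give.

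**Working it through.** The protocol states no power, effect size, SD or correlation for the biomarkers, so there is no figure of its own to reproduce.

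**Inputs from the protocol:** up to 15 subjects at 2:1, so 10 v 5; two-sided alpha 0.05; t-test on change, with 10 + 5 - 2 = 13 degrees of freedom.

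**Assumed, not in the documents:** baseline-to-follow-up correlation r; log-scale SD; equal SDs at baseline and follow-up; lognormal values for the scale comparison.

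**Scale of the problem.** At 10 v 5 with 13 degrees of freedom, 80% power needs a true difference of about 1.66 SD of whatever variable is analysed.

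**Step 1: baseline adjustment alone, same scale.** With outcome variance s²:
- change score: 2(1 - r)s²
- ANCOVA: (1 - r²)s²
- information kept by the change score: (1 - r²) / [2(1 - r)] = (1 + r)/2

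The change score is less precise than ignoring baseline when 2(1 - r) > 1, that is, when r < 0.5. ANCOVA pays a small-sample price for chance baseline imbalance, a factor of 1 + 1/(n - 4) = 1 + 1/11 = 1.091 at n = 15. Multiplying:

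| r | (1 + r)/2 | × 1.091 | Information lost by change score |
|---|---|---|---|
| 0.3 | 0.65 | 0.709 | 29% |
| 0.5 | 0.75 | 0.818 | 18% |
| 0.7 | 0.85 | 0.927 | 7% |
| 0.9 | 0.95 | 1.036 | none (about -4%) |

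**Step 2: adding the log scale.** Lognormal biomarkers were simulated at 10 v 5 with a true 75% reduction (ratio 0.25) and r = 0.5:

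| Assumed log-SD | Power, t-test on raw change | Power, ANCOVA on logs |
|---|---|---|
| 0.3 | 99% | 100% |
| 0.5 | 76% | 100% |
| 0.8 | 38% | 89% |
| 1.0 | 24% | 73% |

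At log-SD 1.0 a t-test on the change in logs has about 65% power. Of the gap of 73 - 24 = 49 points, about 65 - 24 = 41 come from the scale and 73 - 65 = 8 from the adjustment.

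**Step 3: information kept by raw change relative to log ANCOVA.** Here r = 0.5 and the effect is set so that log ANCOVA has about 80% power:

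| Assumed log-SD | True increase | True decrease |
|---|---|---|
| 0.3 | 83% | 61% |
| 0.5 | 70% | 46% |
| 0.8 | 44% | 29% |
| 1.0 | 30% | 22% |
| 1.5 | 9% | 10% |

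Raw change loses more than half of the information in both directions only at a log-SD of about 0.8 or more.

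**Step 4: validity.** With no true effect, the raw-change t-test rejected in 2.9% to 5.1% of simulated trials across all settings, and log ANCOVA in about 5%.

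**The case against.** The strongest reply has four parts.

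- **The rule does not name biomarkers or say raw.** Section 10.3 speaks only of quantitative efficacy variables, and a t-test on the change in log values would fit its wording. Section 10.1 leaves detail to an SAP that is not shown. This stands in part. An untransformed change is the plain reading but not a stated fact, and the SAP could fix the scale. The outcome form and the test, however, are already named without a covariate in both places, so an ANCOVA in the SAP would depart from the protocol text.
- **The skewness is assumed.** This stands. The documents give no biomarker SD, skewness or correlation. At log-SD 0.3 the raw-change test already detects a 75% reduction with about 99% power.
- **The baseline part is modest.** This stands. With r of 0.5 or more, a t-test on log change keeps about 81% or more of the log-ANCOVA information, and at r = 0.9 adjustment gains nothing.
- **Little rests on these tests.** The primary endpoints are safety and feasibility, the biomarkers are exploratory, and group summaries and subject-level data remain for re-analysis. This limits the weight of the point. It does not remove it, because section 10.3.2 counts the exploratory p-values in the overall evidence on safety and effectiveness.

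A reader might infer that the stated test wastes most of the information in 15 subjects. The documents do not support that. For non-negative r, omitting baseline adjustment costs at most half, and a larger loss needs an untransformed analysis and a log-SD that has to be assumed. Nor may a reader infer that the p-values are invalid, since type I error is not inflated.

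**Conclusion.** The point holds as a matter of efficiency. The protocol names an unadjusted change-from-baseline t-test, and the biomarkers are the only listed quantitative efficacy or exploratory outcome on which it can operate. At 10 v 5 with equal SDs, failing to adjust for baseline costs about 7% to 29% of the information for r from 0.7 to 0.3, and nothing at r = 0.9. Any gain from the log scale comes on top and ranges from negligible to large over log-SD 0.3 to 1.0. Its size rests wholly on assumed skewness and on reading the change as untransformed. The trial's primary conclusions are unaffected. The change is still worth making, because the baseline sample is already being drawn and the remedy is nearly free.

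**What to change.** In section 10.3, for the biomarkers, replace the change-from-baseline t-test with ANCOVA at each post-treatment time point: log-transformed value as outcome, treatment and log baseline as terms. Report the ratio of geometric means (ADRC to control) with its 95% CI. Bring the Statistics row of the Protocol Summary into line, and carry the same wording into the SAP before database lock.

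The cost is a wording change and one degree of freedom (13 to 12). No new samples, visits or subjects are needed.

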## **5 ENROLLMENT**

### **5.1 Subject Enrollment**

Subjects are considered enrolled in this study when all of the following have occurred:

1. Written informed consent is obtained
2. All inclusion criteria and no exclusion criteria have been met
3. All screening evaluations are complete
4. Commencement of fat harvest (except for usual care control subjects who will not undergo a lipoaspirate procedure)

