### ***8.7.1.3 Fat Harvest Stopping Rules***

The physician performing the fat harvest procedure should continuously monitor the patient for signs of significant bleeding from the puncture site(s) and overall hemodynamic stability. The tissue harvest procedure should be terminated if any of the following occur:

- Drop in systolic blood pressure < 90 mm/Hg requiring pressor support
- Profuse or uncontrollable bleeding from the puncture site(s)
- Rapid expansion of subcutaneous space at the fat cell tissue harvest site(s) related to bleeding into the subcutaneous space
- Hemoperitoneum or pneumoperitoneum
- Hemothorax or pneumothorax
- Evidence of perforation of a vascular structure that requires ligature or surgical control
- Evidence of perforation into abdominal cavity, peritoneum or gastrointestinal organ

Should any of the above occur, the fat harvest procedure should be terminated and the patient treated according to standard of care. DO NOT PROCEED WITH ADRCs ADMINISTRATION. Complete the study specific SAE form and notify the sponsor within 24 hours.

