### ***8.7.3 ADRCs Delivery***

If subjects become hypotensive and require vasopressors to maintain organ perfusion between the collection of lipoaspirate and the intravenous introduction of ADRCs DO NOT PROCEED WITH ADRCs ADMINISTRATION.

Sterile technique should be maintained throughout the procedure. The intravenous ADRCs infusion will be administered by peripheral intravenous administration. An intravenous catheter (20 or 22 gauge) will be used to administer the ADRCs. The 5 mL output from the Celution System will be diluted to achieve 10 mL lactated Ringer's solution containing  $20 \times 10^6$  ADRCs in a sterile syringe. The syringe will be attached to the sterile macro (part # or designation) syringe filter and the contents of the syringe will be injected into the catheter slowly. The catheter will be flushed with 5 mL of lactated Ringer's solution from a separate sterile syringe.

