#### **10.5 Withdrawal, ITT, PTE**

Reasons for withdrawal pre- and post-randomization will be summarized. The treatment analyses will be performed on intent-to-treat basis as well as on a per-treatment-evaluable basis, as defined below:

Intent-to-Treat (ITT): All randomized subjects; randomization will occur on procedure day prior to the tissue harvest procedure. Subjects will be included in the analysis according to the treatment assigned if population is different than PTE.

Per-Treatment-Evaluable (PTE): All enrolled subjects who have day 5 follow-up information available.

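### The per-treatment set drops ADRC-arm subjects who got no cells only when the cells failed release; those stopped for clinical reasons stay in it

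*Protocol*

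**What the plan says.** **The rule for untreated subjects.** Section 10.3 covers subjects randomized to ADRCs "who undergo liposuction but who are not treated with ADRCs because the ADRCs do not meet release criteria may be followed up". It keeps them in the feasibility analysis, analyses them separately for safety, and for efficacy has them "c) analyzed in the ITT group for efficacy, and (d) excluded from the PTE group for efficacy".

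**Other routes to no infusion.** Section 8.7.1.3 lists events that end the harvest. The first is "Drop in systolic blood pressure < 90 mm/Hg requiring pressor support"; the others concern bleeding, perforation and air or blood in a body cavity. It continues: "Should any of the above occur, the fat harvest procedure should be terminated and the patient treated according to standard of care", and ADRCs are not to be given. Section 8.7.3 withholds the infusion on a separate ground: "If subjects become hypotensive and require vasopressors to maintain organ perfusion between the collection of lipoaspirate" and the infusion. Neither section names an analysis set.

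**Enrollment.** Under section 5.1 the last condition is "Commencement of fat harvest (except for usual care control subjects who will not undergo a lipoaspirate procedure").

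**PTE.** Section 10.5 defines it as "All enrolled subjects who have day 5 follow-up information available". The protocol summary says the "population will include all enrolled subjects who have day 6 follow-up information available". Neither version mentions receipt of ADRCs. The only other stated PTE exclusion is use of a prohibited medication (8.4.1), and vasopressors are not on that list.

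**Role of the sets.** Section 10 makes ITT the primary population and presents the analysis in PTE as well.

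**The concern.** A per-treatment set is read as describing what happens to subjects who received the treatment. Here its membership depends on why the infusion did not take place. Two ADRC-arm subjects can both have been harvested, both have received no cells and both have follow-up, yet one is out of PTE and the other is in. The protocol gives no reason for the difference.

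The subjects left in also fit neither side of the comparison. The summary compares subjects receiving ADRCs plus a graft with usual care controls, and section 10.3 compares usual care with usual care plus ADRCs. A subject who was harvested but not infused belongs to neither group as described.

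The separate safety analysis is limited in the same way. It is given to release failures but not to subjects whose harvest was stopped, although section 8.7.1.3 requires a serious adverse event form for exactly those subjects.

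**Working it through.** The protocol gives no power calculation or other figure to reproduce here: up to 15 subjects, stated in 10.2 not to be powered. The check traces each route through the definitions and then illustrates the size.

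**Step 1. Trace each route for an ADRC-arm subject with day 5/6 data.**

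| Route to no infusion | Source | Enrolled (5.1)? | Meets PTE definition (10.5, summary)? | Excluded from PTE by a stated rule? | Result |
|---|---|---|---|---|---|
| Cells fail release | 7.1.1, 7.2 | Yes | Yes | Yes, 10.3 (d), for efficacy | Out |
| Harvest terminated | 8.7.1.3 | Yes, harvest had begun | Yes | No | In |
| Infusion withheld for hypotension | 8.7.3 | Yes, harvest was done | Yes | No; vasopressors not listed in 8.4.1 | In |

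Two limits apply. A subject without day 5/6 data falls out of PTE anyway. A subject whose harvest never starts is not enrolled and is in ITT only.

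**Step 2. Weight of one subject.** Up to 15 subjects at 2:1 gives 15 × 2/3 = 10 ADRC and 5 usual care. One uninfused subject in PTE is 1/10 = 10% of the ADRC arm. Assume that subjects weigh equally and that an uninfused subject gains no benefit from the cells. Then k such subjects leave a fraction 1 − k/10 of a mean effect:

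- k = 1: 90%
- k = 2: 80%
- k = 3: 70%

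Excluding them would leave 9, 8 or 7 ADRC subjects in PTE.

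**Step 3. How often it might arise.** The protocol gives no rate of such stops, so the rates p below are assumptions. The chance of at least one among 10 is 1 − (1 − p)^10.

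| Assumed p | Calculation | At least one of 10 |
|---|---|---|
| 1/344 = 0.3% | 1 − (343/344)^10 | 3% |
| 5% | 1 − 0.95^10 | 40% |
| 10% | 1 − 0.90^10 | 65% |
| 20% | 1 − 0.80^10 | 89% |

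The first row uses section 9.3, which reports one related serious event among 344 subjects harvested in earlier trials with the system. It is not a rate of harvest stops or withheld infusions. Section 9.10 adds that the safety of liposuction in burn patients has not been established. The true rate may therefore be higher than 0.3%, but the protocol does not support any particular value.

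**The case against.** The best defence is that this is a small drafting gap in a supporting set. ITT is primary, the study tests no powered hypothesis, exclusion (d) concerns efficacy only, and section 10.1 leaves the detailed analyses to an SAP that is not shown. The point about consequence stands and limits the weight of the finding. The appeal to the SAP stands only in part. The protocol itself defines PTE and itself writes a rule for uninfused subjects. An SAP that follows it literally repeats the inconsistency, and one that does not departs from the protocol's definition.

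Four stronger readings are tempting, and the protocol does not support them:

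- *That these subjects are counted as treated.* No sentence assigns them to the treated group within PTE. Analysis by assigned treatment is stated under ITT only. The plan keeps them in the set and does not say where they belong.
- *That the feasibility denominator is open, so that one subject could shift feasibility by 10 points.* Feasibility is a primary endpoint, ITT is the primary set and includes everyone randomized, and 4.6.1 and 10.3.1 judge feasibility step by step. A stopped harvest or withheld infusion is a failure at its step under any reading.
- *That nobody has to follow these subjects.* The visit schedule in 4.1 and Appendix A applies without regard to infusion, and neither 5.5 nor 8.11 makes non-infusion a ground for withdrawal. Serious events are followed under 11.2, and 10.3.1 reports harvest-related events separately. That report separates events by cause, however, and not subjects by whether they were infused.
- *That they are the sickest subjects.* The protocol offers nothing on this.

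**Conclusion.** The point holds as an inconsistency between the PTE definition and the exclusion in 10.3. Followed literally, the plan keeps in PTE any ADRC-arm subject whose harvest was terminated or whose infusion was withheld, provided day 5/6 data exist. It removes for efficacy a subject in the same state whose cells failed release. It also gives the separate safety analysis only to the latter.

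Each such subject is about 10% of the arm's PTE set, assuming full enrollment at 2:1. How many there will be cannot be derived from the protocol. The chance of at least one runs from about 3% to 89% over assumed rates of 0.3% to 20%. The effect on conclusions is modest because PTE only supports ITT in an unpowered study. The correction is still worth making, because a stated rule yields a per-treatment set that does not match its name.

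**What to change.** 1. **Section 10.3:** apply consequences (a) to (d) to every ADRC-arm subject who did not receive the infusion, whatever the reason, naming harvest termination (8.7.1.3), withheld infusion (8.7.3) and release failure. For feasibility this only makes explicit what ITT already implies.
2. **Section 10.5 and the summary:** require that ADRCs were infused for an ADRC-arm subject to enter PTE. Use one follow-up day in both places; they now say day 5 and day 6, while Appendix A schedules a visit at the first dressing change and has no column for either day.
3. **Follow-up wording:** section 10.3 makes follow-up after release failure optional, whereas 7.1.1 and 7.2 state it as definite for viability and Gram stain failures. These passages must be reconciled.

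The cost is a few sentences in the analysis sections and the summary. The PTE ADRC group may lose one or two subjects. No dose, stopping rule or other clinical rule changes.
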